1.0 ETHICS

1.1 Human Research Ethics Committee (HREC)

An appropriate HREC will approve the protocol and the Informed Consent Form before the study is initiated at the study center. Documentation of this approval will be provided to the Sponsor and/ or the Sponsor's designee. The Investigator(s) will have the following responsibilities:

- █ [REDACTED]
- █ [REDACTED]
- █ [REDACTED]
- █ [REDACTED]
- █ [REDACTED]
- █ [REDACTED]
- █ [REDACTED]
- █ [REDACTED]
- █ [REDACTED]

1.2 Ethical Conduct of the Study

This study will be conducted in accordance with the Declaration of Helsinki (see Appendix 1), its revisions and ICH guidelines for Good Clinical Practice (GCP) governing the conduct of studies, and all applicable local regulations including the National Statement on Ethical Conduct in Human Research of the NHMRC. [REDACTED]

[REDACTED]

[REDACTED]

[REDACTED]

1.3 Participant Information and Informed Consent Form

Prior to any study specific screening procedures, the Investigator will explain to each participant or medical treatment decision maker the nature of the study, its purpose, procedures to be performed, the necessity for withdrawal of prohibited medication, expected duration, and the benefits and risks of study participation. After this explanation and before any study specific procedures are performed, the subject or medical treatment decision maker must voluntarily sign an informed consent statement

in the presence of a witness, if applicable (see Appendix 2). The inclusion and exclusion criteria will be reviewed at Day 0 prior to study medication administration.

1.4 Protocol Amendments

Changes in any portion of this protocol will be documented in the form of a protocol amendment and signed revision, signed by the appropriate CLINUVEL PHARMACEUTICALS LIMITED personnel and the Investigator.

Depending on the requirements of the study center’s HREC and the relevant Competent Authority, where applicable, protocol amendment(s) will either need to be submitted for approval or advised by notification. Where formal approval is required, the revision(s) will not be implemented until approval has been obtained.

3.0 INTRODUCTION AND STUDY RATIONALE

Stroke is the second commonest cause of death globally and the leading cause of adult neurological disability¹. Acute arterial ischaemic stroke (AIS), due to arterial occlusion, accounts for 85% of all acute strokes whilst 15% of acute strokes are caused by an acute hemorrhage².

The outcome of AIS, both in terms of disability and survival, can be improved by reperfusion therapy using intravenous thrombolysis³ (IVT) and, or thrombectomy⁴ (mechanical endovascular removal of thrombus), in selected patients, where occlusion involves a proximal vessel of the circle of Willis. Both treatments are time dependent⁵ and at best only a significant minority of patients with AIS, [REDACTED] are eligible for reperfusion treatments. [REDACTED]

[REDACTED] Perfusion brain imaging, with computed tomography (CT) or Magnetic resonance imaging (MRI), has become the cornerstone of selecting AIS patients for reperfusion therapy and as such individualized patient treatment by using imaging as a surrogate for a ‘brain tissue clock,’ as opposed to arbitrary time since last seen well, in treatment decision paradigms⁶⁻⁹.

Stroke unit care has been shown to reduce mortality and dependence in AIS [REDACTED]

More than ever, effective neuroprotection – that may either facilitate more patients being suitable for timely reperfusion therapy by slowing the conversion of penumbra to core, or intrinsically attenuate the size of a threatened area of cerebral infarction is needed to aid assist in treating the global burden of disease due to AIS.

BLOOD BRAIN BARRIER (BBB)

It is well published that after a cerebrovascular accident (stroke) the damage to the blood-brain-barrier (BBB) includes decreased expression and altered organization of tight junction constituent proteins but also modulation of functional expression of endogenous BBB transporters.

Several hallmarks of pathology following ischaemic stroke is breakdown of the BBB, resulting in increased paracellular solute leak, modulation of transport proteins and endocytotic transport mechanisms, and inflammatory damage. Such barrier breakdown leads to a significant increase in paracellular permeability at the level of the cerebral microvasculature. These pathological derangements variably result in cognitive and motor impairments.

One of the most significant contributors to BBB breakdown in stroke is activation of proteinases such as matrix metalloproteinases (MMPs). This includes MMPs that are activated by hypoxia-inducible factor-1 α (HIF-1 α)-dependent mechanisms (i.e., MMP-2) and MMPs whose activation is triggered by cytokines (i.e., TNF- α , IL-1 β) such as MMP-3 and MMP-9.

Integrins, transmembrane glycoprotein receptors for the extracellular matrix, also play a significant role in BBB breakdown. Physiologically, integrins interact with constituents of the basement membrane (i.e., collagen IV, fibronectin, laminin, heparin sulfate proteoglycans such as perlecan) to regulate BBB permeability and transport. In ischaemic stroke, integrins are rapidly degraded, which leads to BBB breakdown and subsequent edema, inflammation, and exacerbation of stroke injury.

[REDACTED]

[REDACTED]

[REDACTED]

[REDACTED]

[REDACTED]

[REDACTED]

[REDACTED]

[REDACTED]

[REDACTED]

[REDACTED]

[REDACTED]

In 111 patients a longitudinal study showed that the effect of early plasma α -MSH on stroke outcome was more than a reflection of the stress response related to stroke severity and that maintenance of plasma α -MSH after stroke onset could be protective. Furthermore, a growing body of experimental data has shown that exogenous administration of α -MSH decreases infarct volume and improves stroke outcome¹⁶. There are numerous mechanisms by which α -MSH (and related neuropeptides) could improve stroke outcome, and these effects are mediated through 5 different melanocortin receptors (MCRs). Potent antipyretic properties of α -MSH, which could potentially be capitalized on in the treatment of stroke, are mediated through the MCR3/MCR4 receptor complex in the brain.

OBJECTIVES

The objective of this pilot study is to evaluate the safety of afamelanotide, identify changes in reperfusion in AIS patients, specifically the ischaemic core and/or the penumbral ischaemic zone (salvageable tissue) and assess neurological functions and activities of daily living in AIS patients.

SCIENTIFIC HYPOTHESIS

The scientific hypothesis is that the pharmacologic intervention with afamelanotide would positively affect the infarcted area in patients with AIS [REDACTED]

Afamelanotide is a potent synthetic analogue of the naturally occurring hormone, alpha melanocyte stimulating hormone (α -MSH).

[REDACTED]

[REDACTED]

[REDACTED]

[REDACTED]

[REDACTED]

[REDACTED]

[REDACTED]

[REDACTED]

[REDACTED]

[REDACTED]

Afamelanotide 16mg has been shown to be effective in providing systemic photoprotection in EPP and has obtained marketing authorization in the European Union (October 2014) and the United States (October 2019) for the prevention of phototoxicity and endothelial damage incurred by adult EPP patients. The results of the clinical trials conducted by CLINUVEL, as well as of one long term observational study and the ongoing post-authorization pharmacovigilance activities, confirm the positive safety profile of afamelanotide to date¹⁷⁻¹⁹. [REDACTED]

[REDACTED]

[REDACTED]

[REDACTED]

[REDACTED]

It is proposed for AIS patients diagnosed with an acute stroke - and not eligible for intravenous thrombolysis (IVT) or endovascular thrombectomy (EVT) - originating from distal occlusion (M2 and beyond) of the large vessels be enrolled [REDACTED]

[REDACTED]

[REDACTED]

[REDACTED]

4.0 STUDY OBJECTIVES

4.1 Primary Objective

The objective of this pilot study is to evaluate the safety of afamelanotide in AIS patients.

4.2 Secondary Objectives

The secondary objectives of this pilot study CUV801 are to identify changes in reperfusion of the ischaemic core and ischaemic penumbra (salvageable tissue) in AIS patients with distal occlusion of the large vessels and who are ineligible to receive IVT or EVT, and to monitor changes in neurological function, cognitive functions and changes of daily activities in these patients.

5.0 INVESTIGATIONAL PLAN

5.1 Overall Design and Plan of the Study

This is an open label phase IIa pilot study to be conducted in six (6) patients with acute AIS during a 6-weeks period [REDACTED]

To determine eligibility for entry into the study, [REDACTED]
[REDACTED] Eligible patients will be enrolled and will be administered [REDACTED]
[REDACTED]

[REDACTED]

[REDACTED]

The results will be reviewed on the basis of a benefit: risk assessment. If the benefit: risk assessment is in favour of afamelanotide, in the opinion of the Investigator, [REDACTED]

Radiological evaluation by assessing the imaging from Computed Tomography Perfusion (CTP)

Clinical evaluations will be performed by accredited study staff over the course of the study. The NIHSS will be performed at the Day of Admission (Day 0) and on Days 1, 2, 3, 4, 7, 8 and 42 or Premature Termination Visit (if applicable). The modified Rankin Scale (mRS) will be performed on Days 0, 7 and 42 or Premature Termination Visit (if applicable). [REDACTED]

Safety assessments (review of AEs and concomitant medications) will be carried out each day (each study visit from the Day of Admission to Day 8 and Day 42 or Premature Termination Visit).

5.2 Selection of Study Population

The target population consists of male and female patients with AIS due to acute distal (M2 and beyond) large vessel occlusion (LVO) or perforator occlusion and who are ineligible to receive IVT or EVT. The following inclusion and exclusion criteria must be met by each patient before enrollment in the study.

5.2.1 Inclusion Criteria

The patients have to fulfill all of the following *inclusion criteria* for study participation:

5.2.4 *Withdrawals and Replacement of Patients*

A discontinuation occurs when a patient does not complete the study as required by the study protocol. Patients will be free to discontinue their participation in this trial at any time for any reason. In addition, patients may be withdrawn from the trial at the discretion of the Investigator or medically qualified nominee. A patient may be withdrawn for any of, but not limited to, the following reasons:

- Informed consent withdrawn by the patient or medical treatment decision maker;
- AE requiring study discontinuation;
- When the Investigator's or nominee's best professional judgment would indicate that it would be in the patient's best interest to be withdrawn;
- Violation of inclusion/exclusion requirements.

The reasons for withdrawal or discontinuation of a patient will be recorded in the patient's medical notes and CRF. If an AE is the reason for discontinuation, the event must be followed up and documented as described in the 5.5.3.2 Safety variables of the protocol. If the patient discontinued for any reason after the enrolment into the study, a study Premature Termination visit, as described in 5.5.1, should be performed at the time of study discontinuation, or as soon as possible after discontinuation. This visit will be documented in the patient's medical notes and CRF.

Any patient(s) withdrawn from the trial prior to their completion for any reason will not be replaced. Data compiled to the point of discontinuation will be used for 'intent to treat' (ITT) analysis. Patients violating any of the inclusion and exclusion criteria will be described as protocol deviators.

5.3 **Study Medication**

5.3.1 *Description of Study Medication*

[REDACTED] afamelanotide
[REDACTED]
[REDACTED]

5.3.2 *Treatment Groups*

There is one treatment group in this study (Open-label study). As such, all patients who satisfy the inclusion/exclusion criteria will be allocated a study subject number and receive afamelanotide. Study subject number allocation will be detailed in the CUV801 Study Operating Manual (SOM).

The groups consist of:

- **Six (6) stroke patients with acute distal (M2 and beyond) LVO or perforator occlusion.**

Open label study: Six (6) patients receiving afamelanotide.

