5.5.3.2.5 Adverse Events

An adverse event (AE) is defined as any untoward medical event (clinical or laboratory) experienced by a patient during the course of a clinical trial, whether or not it is related to the investigational product. An AE may be a symptom, sign, or abnormal finding or test result. Whenever possible, the Investigator will group together into a single term, signs and symptoms that constitute a single diagnosis. For example, cough, rhinitis and sneezing might be grouped together as "upper respiratory tract infection".

The Investigator will monitor each patient closely for the development of AEs, and any adverse experience spontaneously reported by or elicited from the patient or observed by the Investigators (physician or study staff) will be recorded in the patient's medical notes and on the appropriate AE page of the CRF, when applicable. [REDACTED]

[REDACTED]
[REDACTED]
[REDACTED]

[REDACTED] It is the responsibility of any member of the study site staff to immediately report any suspected AE to the Investigator.

The Investigator will assess the AE(s) in the patient's medical notes and provide the date and time of onset, severity, seriousness, action taken, outcome, date of resolution (or comment that the event is still continuing) and relationship to study medication.

If a laboratory value is outside the normal range, the Investigator must comment on the findings in the laboratory report. For any clinical laboratory abnormality, the Investigator will make a judgment as to clinical significance. All clinically significant laboratory abnormalities will be recorded as an AE in the patient's medical notes and on the AE page of the CRF.

All AEs will be followed up in accordance with GCP. AEs will be graded for severity as defined below:

- **Mild** - The AE is transient and easily tolerated by the patient. Specific action is optional;
- **Moderate** - The AE causes the patient discomfort and interrupts the patient's usual activities;
- **Severe** - The AE causes considerable interference with the patient's usual activities and may be incapacitating or life-threatening.

Outcome of the event must be described as one of the following:

- Recovered without sequelae;
- Recovered with sequelae;
- Recovering;
- Not recovered;
- Death.

The Investigator will be asked to document his/her opinion of the relationship of the event to the study drug as follows:

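### In the legible text, a dosed patient withdrawn by the Investigator can have no Day 42 assessment, although the primary endpoint runs to Day 42

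*Combined protocol and SAP*

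**What the plan says.** **Withdrawal.** Section 5.2.4 lets the Investigator withdraw a patient for an AE, in the patient's best interest, or for an eligibility violation. Consent withdrawal is a separate reason. On leaving, "a study Premature Termination visit, as described in 5.5.1, should be performed at the time of study discontinuation" or as soon as possible after that. Withdrawn patients are not replaced. On use of the data, the section says "Data compiled to the point of discontinuation will be used for" the intention-to-treat analysis.

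**Schedule.** Section 5.1 pairs Day 42 with the early visit for all three assessments:
- AE and concomitant medication review: "each study visit from the Day of Admission to Day 8 and Day 42 or Premature Termination Visit".
- NIHSS, after Day 0: "on Days 1, 2, 3, 4, 7, 8 and 42 or Premature Termination Visit (if applicable").
- mRS: "The modified Rankin Scale (mRS) will be performed on Days 0, 7 and 42 or Premature Termination Visit (if applicable").

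**Endpoints and populations.** Section 5.7.2.1 defines the primary endpoint as TEAEs recorded on dosing days and through Day 42. The synopsis names Day 42 among the NIHSS and mRS comparisons with baseline. The Safety Population is every enrolled patient (5.7.5.1), and safety summaries are based on it (5.7.5.7).

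**Follow-up duties that can be read.** If an AE causes discontinuation, "the event must be followed up and documented" (5.2.4). Section 5.5.3.2.5 adds: "All AEs will be followed up in accordance with GCP". It also requires SAEs occurring in the course of the study to be reported within 24 hours, and clinical observation of the patient for as long as needed. Section 5.7.5.11 allows AE review between visits at the Investigator's discretion.

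**The concern.** The endpoint window closes at Day 42, but the schedule lets a termination visit in the first days take the place of Day 42. None of the legible follow-up duties says that new non-serious TEAEs, or NIHSS and mRS at Day 42, are collected once the Investigator has withdrawn the patient.

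Two features make this matter. First, the patient remains in the safety denominator, so a late event that nobody records is counted as no event, and the incidence can only be understated. Second, the loss is related to outcome. A patient taken out because of an AE is more likely than the others to do badly later. With six patients and no replacement, each one is a sixth of the data.

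**Working it through.** The plan has no figure to reproduce: Section 5.7.4 sets the six patients by availability, without a power, event-rate or dropout input. The check compares the rules and then sizes the consequence of one withdrawal.

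**1. What each legible rule covers after withdrawal by the Investigator**

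| Item | Legible rule | Covered to Day 42? |
|---|---|---|
| AE that caused withdrawal | followed up (5.2.4) | yes, that event |
| AEs already recorded | followed up under GCP (5.5.3.2.5) | yes, no end day stated |
| SAEs, including death | reported if they occur in the course of the study (5.5.3.2.5) | not stated for a withdrawn patient |
| New non-serious TEAEs | none | no |
| Day 42 NIHSS and mRS | Day 42 or the early visit (5.1) | no |

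**2. Scheduled AE reviews lost**

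The legible AE review days are 0, 1, 2, 3, 4, 7, 8 and 42 (synopsis). The withdrawal day is an assumption.
- Leaves on Day 1: reviews on Days 2, 3, 4, 7, 8 and 42 remain undone, six in all.
- Leaves on Day 4: Days 7, 8 and 42, three in all.
- Leaves on Day 8: Day 42 only. That one review has to account for 42 − 8 = 34 days, even in a patient who completes the study.

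**3. Effect on a TEAE count**

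If the withdrawn patient later has an event with a preferred term not already recorded for that patient, and it is missed, the incidence for that term is too low by 1/6 = 16.7 percentage points.

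**4. What zero events would rule out (illustration, not a planned analysis)**

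The one-sided 95% exact upper limit for zero events in n patients is 1 − 0.05^(1/n).
- n = 6: 1 − 0.05^(1/6) = 0.393, or 39.3%.
- n = 5: 1 − 0.05^(1/5) = 0.451, or 45.1%.

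**5. Day 42 scores (illustration)**

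Section 5.7 says the statistics are non-parametric, and the synopsis uses a two-sided 0.05 level. The test itself is not legible. If it were a paired signed-rank test, the smallest two-sided exact p would be 2/2^n: 2/64 = 0.031 with six Day 42 values and 2/32 = 0.0625 with five. One missing Day 42 value would then put 0.05 out of reach.

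**The case against.** The strongest objection is redaction. The sentence in 5.2.4 refers to 5.5.1 for the content of the termination visit, and that section is blacked out. So are part of the AE-recording text in 5.5.3.2.5, the missing-data rules in 5.7.5.3 and part of 5.7.5.11. Reporting details are deferred to the Study Operating Manual, and the consent elements in the appendices call for a description of how participation ends. A follow-up rule may sit in any of these. This stands, and it limits the point to the legible text.

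Four stronger readings are tempting, and the documents do not support them.
- *The plan stops all safety follow-up at withdrawal.* It does not say so. The causal AE is followed, recorded AEs are followed, and the SAE rule is not restricted to patients still participating. The TEAE window to Day 42 also carries no stated exception for withdrawn patients.
- *Later data are excluded from analysis.* Section 5.2.4 says data up to discontinuation will be used; it does not say that only those data will be. The sentence also concerns the intention-to-treat set, which is the efficacy population, not the safety set.
- *An early score will be analysed as the Day 42 score.* Section 5.1 says when assessments are performed. How a missing Day 42 value is handled is in redacted text.
- *A Day 8 withdrawal loses 34 days of continuous AE collection.* Patients who complete have no legible scheduled AE review between Day 8 and Day 42 either. The loss is one scheduled review.

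A reader may also note that stopping treatment and leaving the study look separate, since 5.7.5.8 tabulates early termination of treatment. In the one legible case, pregnancy or breastfeeding (5.5.3.2.5), stopping treatment leads to the same termination visit.

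After all this, the wording of 5.1 and the timing in 5.2.4 remain legible, and together they allow a withdrawn patient to have no Day 42 assessment.

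**Conclusion.** The point holds as a cheap improvement. It concerns dosed patients withdrawn by the Investigator; after consent is withdrawn, further collection may not be possible. The clear gap is new non-serious TEAEs and Day 42 NIHSS and mRS. Whether SAEs after withdrawal are covered is not stated.

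One withdrawal by Day 8 loses the only legible scheduled AE review after Day 8 in one of six patients. The zero-event upper limit moves from 39.3% to 45.1% if that patient is not followed to Day 42. These figures assume a single withdrawal on an assumed day, and the number of withdrawals cannot be predicted. No size is given for a shift in the Day 42 scores, because that would require an imputation rule that cannot be read. No stated figure in the plan is wrong, and the study is descriptive. Confidence is medium because the redacted sections may already settle the matter.

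**What to change.** In 5.1 and 5.2.4:
- Make the Premature Termination Visit additional to Day 42, not an alternative to it.
- State that any dosed patient who stops afamelanotide, or is withdrawn by the Investigator, continues AE and SAE collection to Day 42 and has NIHSS and mRS at Day 42.
- Allow three exceptions: consent to follow-up is withdrawn, the patient dies, or the visit itself would be against the patient's interest. In the last case, obtain the information by telephone or from records where consent allows.
- Include all data collected to Day 42 in the safety and intention-to-treat analyses, and do not analyse an earlier score as Day 42.

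If redacted text already contains such a rule, only the wording of 5.1 and 5.2.4 needs to be aligned with it.

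The cost is a few sentences in an amendment that may need ethics committee approval (1.4). Each withdrawn patient, at most six, would also need continued AE/SAE follow-up and either the already scheduled Day 42 visit or a telephone or records check.

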5.3.3 Dosage and Administration of Study Medication

Afamelanotide [REDACTED] will be administered [REDACTED] on the designated study days. [REDACTED]

[REDACTED]. Please refer to the CUV801 SOM for further details.

[REDACTED]
[REDACTED]
always within 24 hours of onset of symptoms or last seen well.

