5.7.3.1 Specification of Safety Endpoint (Primary Endpoint)

The safety endpoint will be the incidence of TEAEs occurring during the study period, including clinically significant changes in laboratory parameters, will be listed by intensity, seriousness, outcome, and relationship to study drug.

5.7.4 *Sample Size*

While this is a phase IIa study of common indication, the sample size is based on availability of patients. A total of six (6) patients are planned to be enrolled in this study. This constitutes an open-label exploratory study.

5.7.5 *Analysis Plan*

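### Section 5.2.4 bars replacement even before the first dose, so six enrolled does not secure six patients receiving afamelanotide (minor)

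*Combined protocol and SAP*

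**What the plan says.** Section 5.2.4 (Withdrawals and Replacement of Patients) sets the rule: "Any patient(s) withdrawn from the trial prior to their completion for any reason will not be replaced". It covers every reason and every time before completion. The reasons it lists include withdrawn consent, an adverse event, the investigator's judgement and "Violation of inclusion/exclusion requirements", and the list is not exhaustive.

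The target number is given in two ways. Section 5.3.2, like the synopsis, says "Open label study: Six (6) patients receiving afamelanotide". Section 5.7.4 says "A total of six (6) patients are planned to be enrolled in this study" and explains that "the sample size is based on availability of patients".

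Two places tie enrolment to dosing. Section 5.3.2 says "all patients who satisfy the inclusion/exclusion criteria will be allocated a study subject number and receive afamelanotide". The visible part of 5.3.3 describes administration as "always within 24 hours of onset of symptoms or last seen well".

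Elsewhere the plan treats enrolled and treated as different states. The Safety Population (5.7.5.1) is everyone enrolled. The ITT population (5.7.5.2) is treated patients with a post-dose efficacy assessment. Section 5.7.5.8 foresees serious events before the first dose. Section 5.7.5.7 bases the safety summaries on the Safety Population.

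**The concern.** Refusing to replace patients who have been dosed is sound: it prevents a patient with a poor outcome from being exchanged for another. That reason does not apply before the first dose, when there is no drug outcome to select on. The rule nevertheless treats both cases alike.

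The primary endpoint is the incidence of TEAEs, and each visible limb of the definition in 5.7.5.8 is framed by administration of study medication. An undosed patient therefore cannot have a TEAE. That patient would take one of six places permanently and also remain in the denominator. The safety conclusion rests on the number exposed, so two things are at stake: the precision of a very small safety data set, and the match between the number the plan says will be treated and the number its rules deliver.

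**Working it through.** **The plan's own figure.** N = 6 rests on availability. The visible text gives no event rate, precision target, power or drop-out rate, so there is no calculation to reproduce. What follows is the consequence of the rule.

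**Inputs from the documents.** Six enrolled (5.7.4); six receiving drug (synopsis, 5.3.2); no replacement (5.2.4); safety denominator all enrolled (5.7.5.1, 5.7.5.7).

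**Assumptions, not in the documents.** Chance p that an enrolled patient is never dosed: 3%, 5% or 10%, independent between patients. True event rate for illustration: 20%.

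**Step 1. Chance that at least one of six places is lost:** 1 − (1 − p)^6.
- p = 3%: 1 − 0.97^6 = 16.7%
- p = 5%: 1 − 0.95^6 = 26.5%
- p = 10%: 1 − 0.90^6 = 46.9%

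**Step 2. Chance of seeing at least one event with a true rate of 20%:** 1 − 0.8^n.
- n = 6: 1 − 0.8^6 = 73.8%
- n = 5: 1 − 0.8^5 = 67.2%

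**Step 3. One-sided 95% upper limit when no event is seen:** 1 − 0.05^(1/n).
- n = 6: 39.3%
- n = 5: 45.1%

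**Step 4. Averaging over the assumed loss.** Each place shows an event with probability 0.2 × (1 − p), taking loss as independent of the event. The chance of at least one event is 1 − (1 − 0.2(1 − p))^6.
- p = 0: 73.8%
- p = 3%: 1 − 0.806^6 = 72.6%
- p = 5%: 1 − 0.81^6 = 71.8%
- p = 10%: 1 − 0.82^6 = 69.6%

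**Step 5. Denominator.** With five dosed and one affected, the summary over all enrolled reads 1/6 = 16.7%; among those exposed it is 1/5 = 20.0%. If the undosed patient were replaced but 5.7.5.1 left as it is, seven would be enrolled and six dosed, and one affected patient would read 1/7 = 14.3% instead of 1/6 = 16.7%. Replacement alone does not cure the denominator.

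**The case against.** The strongest reply is that the window is narrow. The plan intends every eligible patient to be dosed, and soon. A reader might infer from 1.3, "The inclusion and exclusion criteria will be reviewed at Day 0 prior to study medication administration", that a patient who fails this review loses a place. The documents do not support that: screening is itself on Day 0, 5.2 requires the criteria to be met before enrolment, and 5.7.5.1 lists patients screened but not enrolled separately. Such a patient is a screen failure and uses none of the six places. What remains is withdrawn consent, clinical change, investigator judgement or a violation found late, between enrolment and the first dose.

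Enrolment is also not defined in the visible text. Several sections that could define it are redacted or not in the extract, and subject number allocation is left to the Study Operating Manual. If enrolment meant receipt of the first dose, the gap would close. The separate use of enrolled and treated in 5.7.5.1 and 5.7.5.2 argues against that reading but does not exclude it.

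Finally, with N set by availability, a no-replacement rule breaks no power or precision claim. This stands, and it limits the weight of the point. It does not remove it: the visible rule is explicit, has no exception before dosing, and can leave fewer than six treated.

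**Conclusion.** The point holds as a minor one. As written, 5.2.4 allows the study to end with fewer than six patients exposed, and 5.7.5.1 keeps an enrolled but undosed patient in the TEAE denominator. If one place is lost, detection of an event with a true rate of 20% falls by about 7 percentage points (73.8% to 67.2%) and the zero-event upper limit rises by about 6 (39.3% to 45.1%). Averaged over assumed loss rates of 3% to 10%, detection falls by about 1 to 4 points. The loss rates and the event rate are assumptions; the documents give neither.

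Three stronger readings are not supported:
- **The two targets contradict each other.** They agree whenever every enrolled patient is dosed, which is what 5.3.2 intends.
- **An undosed patient yields no safety information at all.** Section 5.7.5.8 lists all adverse events and has serious events before the first dose documented in the report. What is missing is information on the safety of afamelanotide.
- **Five patients would put the 0.05 level out of reach for efficacy.** An exact two-sided signed-rank test has a smallest p of 2/2^6 = 0.031 with six pairs and 2/2^5 = 0.0625 with five, but the visible text names no test and calls the analysis exploratory.

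**What to change.** - **5.2.4:** state that a patient withdrawn before the first dose will be replaced, and that a patient who has received any dose will not be.
- **5.7.4:** align the target to six treated patients.
- **5.7.5.1:** define the Safety Population as patients who received at least one dose, with enrolled but undosed patients listed separately.

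If the sponsor prefers to keep no replacement, restate the synopsis and 5.3.2 as six enrolled and up to six treated; the change to 5.7.5.1 is still needed.

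The cost is a short amendment to the wording and possibly one or two extra consents and screenings. The number exposed stays at the planned six, and the protection against selective replacement after dosing is kept.
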